2.2 Primary Aim

The primary aims of the proposed pilot CET are:

1. To establish the feasibility of the CET protocol and procedures in preparation for a full-scale future trial.
2. To generate estimates of the size of the comparative effects of enhanced, cancer-specific smoking cessation treatment versus a generic standard care package similar to quitline care in terms of biochemically confirmed 7-day point prevalence abstinence (no smoking in the past 7 days) 26 weeks after a target quit date.

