3.2 Primary & Exploratory Aims

Primary Aims

Aim 1: To establish the feasibility of the CET protocol and procedures in preparation for a full-scale future trial.

Aim 2: To generate estimates of the size of the comparative effects of intensive, cancer-specific smoking cessation treatment versus a generic, lower-

PROTOCOL TITLE: Comparative Effectiveness Trial of Tobacco Cessation Treatments among Cancer Patients who Smoke

intensity recommended smoking cessation treatment in terms of biochemically confirmed 7-day point prevalence abstinence (no smoking in the past 7 days) 26 weeks after a target quit date.

Exploratory Aims

Aim 3: To estimate differences in CET arms in exploratory outcomes including patient acceptability, completion, adherence, costs, and cost-effectiveness.

Aim 4. To elicit input from patients who have experienced cancer to inform study methods and interventions.

Aim 5. To estimate the extent to which treatment effects on abstinence and exploratory outcomes differ across patient subpopulations based on demographics (age, race, sex, ethnicity, socioeconomic disadvantage); nicotine dependence; and cancer site, stage, and treatment phase.

Aim 4. To explore relations between 1) engagement in tobacco treatment and 2) quitting smoking and health and healthcare utilization outcomes, including cancer outcomes overall, and as a function of environmental exposures and, for those enrolled in the CET, randomly assigned treatment condition.

3.3 Study hypotheses.

The primary hypothesis to be tested for Aim 1 is that at least 12% of eligible adult patients who have cancer and smoke cigarettes and are referred to the tobacco treatment outreach team will initiate an evidence-based form of smoking treatment (either Wisconsin Tobacco Quit Line care or treatment offered in the CET).

The primary hypothesis to be tested for Aim 2 is that more-intensive, cancer-specific smoking cessation treatment will increase the log odds of achieving 7-day abstinence 26 weeks after a target quit date by at least 50% over the comparator condition (predicted odds ratio ≥ 1.50).

Exploratory hypotheses include the following:

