For Aim 3, we hypothesize that the majority of patients assigned to each condition will initiate treatment and will receive at least some counseling and use at least some of the provided medication. We also hypothesize that patient ratings of acceptability and satisfaction will be favorable. We also expect retention, adherence, and satisfaction with treatment to be higher in enhanced care relative to the standard care control condition. We anticipate that the more-intensive treatment, although more costly, will be cost-effective in terms of the incremental cost effectiveness ratio per additional

PROTOCOL TITLE: Comparative Effectiveness Trial of Tobacco Cessation Treatments among Cancer Patients who Smoke

patient who quits smoking, relative to the comparator condition and to other preventive health interventions.

For Aim 4, we are not testing a specific hypothesis. Instead, we are seeking patient input to enhance the acceptability of tobacco treatment outreach and the relevance of smoking cessation counseling for participants in the CET.

For Aim 5, we expect treatment reach to be especially high among historically undertreated populations (including African-American, Medicaid-eligible patients, and those from disadvantaged neighborhoods), and for the effects of enhanced care (vs. the standard care comparator) to be similar across patient subgroups.

3.4 Study endpoints.

Primary endpoints:

1. Reach of smoking treatment, defined as the proportion of eligible patients who initiate evidence-based smoking treatment through the opt-out referral program. (Aim 1)
2. Biochemically verified 7-day point-prevalence abstinence 26 weeks after a target quit date (confirmed by expired carbon monoxide and/or a cotinine urine or saliva sample test). (Aim 2)

Secondary endpoint:

1. Self-reported 7-day point-prevalence abstinence 12 weeks after a target quit date. (Aim 2).

Exploratory endpoints:

1. Treatment acceptability and feasibility indicators including treatment retention (at each treatment contact/milestone) and completion, medication adherence, patient satisfaction, and patient ratings of burden. (Aim 3).
2. Treatment costs from payer and patient perspectives. (Aim 3).
3. Incremental cost-effectiveness ratios for each additional patient who quits smoking with higher-intensity treatment versus lower-intensity treatment. (Aim 4).

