PROTOCOL TITLE: Comparative Effectiveness Trial of Tobacco Cessation Treatments among Cancer Patients who Smoke

- Received care from a participating oncology clinic in the past year.
- Has a current tobacco use status.
- Does not have a preferred language other than English (missing language preference will be included).
- Valid address that is not a correctional facility or residential treatment/care facility.
- No flag for patient cognitive impairment, activated health care power of attorney, or other health care agent (e.g., legally authorized representative) in the EHR.

The following additional inclusion criteria must be met for inclusion in the CET

- Smoked combustible cigarettes in the past month.
- Able to speak and understand English.
- Willing to set a date to quit smoking in the next 60 days.
- Willing to receive smoking treatment information.
- Willing to complete study activities.

For qualitative interviews, the only inclusion criteria are:

- At least 18 years of age.
- Have a history of cancer.
- Willing to participate in an audio-recorded interview about their experiences and perspectives.

5.3 Exclusion criteria. The following exclusion criteria apply to the CET:

- Current suicidal ideation.
- Suicide attempt in the past year.
- Currently receiving treatment for bipolar disorder, schizophrenia, schizoaffective disorder, or psychotic disorder.
- Incarceration.
- Unable to provide informed consent to treatment (i.e., cannot answer questions about study procedures or risks after hearing about the study).

Those who decline the screening invitation or do not meet eligibility criteria will be advised to quit smoking and offered standard smoking cessation treatment (referral to their primary care provider

PROTOCOL TITLE: Comparative Effectiveness Trial of Tobacco Cessation Treatments among Cancer Patients who Smoke

and/or to the Wisconsin Tobacco Quit Line or other tobacco quit line, as appropriate given state of residence).

The only exclusion criterion for qualitative interviews is not being able to provide informed consent due to difficulty understanding the consent information.

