The only biospecimens to be collected in the study will be collected directly from CET participants at the follow-up visit 6 months after a participant's target quit date, if the participant reported no use of tobacco products at the 26-week post-quit-date follow-up call. These participants reporting abstinence from tobacco will be asked to provide a breath sample for CO testing and a single urine sample for cotinine testing at either the UW-CTRI Madison office or at their oncology clinic (if willing to schedule this so it coincides with a clinic visit). Breath samples cannot be stored and urine samples will be tested immediately after collection and then discarded the same day. If patients are unable to travel to Madison for biochemical verification of abstinence, they will be given the option of providing a saliva sample in the mail using a kit supplied by the research team. These kits would be retained only until testing by a lab is complete and would then be destroyed.

3. Drugs.

The medications to be used in this study include transdermal nicotine patches and varenicline. Both medications are approved by the FDA for use as smoking cessation aids. No other medications or devices will be used in the research.

13.4 Data Collection.

• List of data elements.

The following data elements will be extracted from EHR data via CRDS reports. These data elements are needed to enable preparation of initial study recruitment mailings that will let patients know they have been identified for the study and that they can opt out of recruitment calls and letters.

- MRN
- Name
- Phone numbers (with preferred number flagged)
- Address
- City
- State
- ZIP code
- Communication preferences (MyChart, mail, phone)
- Tobacco use status (must be smoking currently)

PROTOCOL TITLE: Comparative Effectiveness Trial of Tobacco Cessation Treatments among Cancer Patients who Smoke

- Preferred language (must be English or missing)
 - Use of smokeless tobacco
 - Use of e-cigarettes
 - Date of birth (must be at least 18 years old)
 - Sex
 - Gender
 - Race
 - Ethnicity
 - Insurance type
 - Assigned primary care provider
 - Oncologist
 - Clinic department (where seen in the past year to achieve eligibility)
 - Cancer diagnosis (diagnosis in past 3 years that conferred eligibility)

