- Other (describe): Saliva samples returned via mail by participants will be stored in a locked cabinet in a locked office until ready to be shipped to a lab for testing. Samples will be identified by a code number only.
- Data will not be stored or accessed on portable devices.
- Portable devices such as laptops will be used to access secure web-based data collection sites such as REDCap. No data will be stored locally on the devices.
- Data stored on portable devices will be coded with the key stored separately. No identifiers will be stored on portable devices.
- Data stored on portable devices and therefore only encrypted devices will be used.

16.4 Management of Identifiers:

- Identifiers will be destroyed after all data has been collected.
- Identifiers will be destroyed at study closure.
- Identifiers will be destroyed at study closure or at the time of publication.

16.5 Data and specimen handling:

1. Data associated with specimens.

A subset of participants in the CET who report no smoking in the past 7 days 26 weeks after their target date to quit smoking and who are unable to come to Madison to provide a breath and urine sample for biochemical verification of abstinence will be sent saliva collection kits identified by a unique code number specific to saliva tests kits. These kits will include instructions for home collection of saliva using the passive drool method, collection materials, and a stamped, addressed return envelope to return samples to the study team. Only the team member

PROTOCOL TITLE: Comparative Effectiveness Trial of Tobacco Cessation Treatments among Cancer Patients who Smoke

coordinating saliva sample collection will have the key to this code, and they will be responsible for entering results from the saliva testing in the REDCap database. This unique key will be destroyed on study closure. No other biospecimens (breath or urine samples) will be banked. These samples will instead be tested immediately and recorded in the REDCap database.

2. **Where and how data or specimens will be stored.**
Saliva samples will be stored in a locked cabinet in a locked office until ready to ship to the lab that conducts the testing and returns results identified only by the unique sample identifier to the saliva collection coordinator for the study.
3. **How long will the data or specimens will be stored.**

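### Section 13.3 ties week-26 specimen collection to no tobacco use although the primary endpoint is no smoking, so a quitter who uses non-combusted tobacco would go untested and be counted as a smoker

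*Combined protocol and SAP*

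**What the plan says.** The combined protocol and SAP defines the Aim 2 outcome in section 2.2 as "7-day point prevalence abstinence (no smoking in the past 7 days) 26 weeks after a target quit date". Section 3.2 repeats it as "biochemically confirmed 7-day point prevalence abstinence (no smoking in the past 7 days) 26 weeks after a target quit date". Section 3.4 adds the means of verification: "confirmed by expired carbon monoxide and/or a cotinine urine or saliva sample test".

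Section 13.3 (item 2, Biospecimens) says who gives specimens. They are collected at the six-month visit "if the participant reported no use of tobacco products at the 26-week post-quit-date follow-up call", and the next sentence repeats the restriction: "These participants reporting abstinence from tobacco will be asked to provide a breath sample for CO testing". The same sentence adds a urine sample. People who cannot travel may mail saliva.

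Section 16.5 describes the recipients of those mailed kits differently, as participants "who report no smoking in the past 7 days 26 weeks after their target date to quit smoking".

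Section 20.6 requires both a report of abstinence and biochemical evidence. Anyone lacking either counts as a smoker in the primary analysis.

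On entry, section 5.2 requires that a trial participant "Smoked combustible cigarettes in the past month". The exclusions in section 5.3 do not mention other tobacco products. The record extraction in section 13.4 includes "Use of smokeless tobacco" and e-cigarette use.

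**The concern.** The behaviour that defines success is not smoking. The behaviour that opens the door to verification in 13.3 is not using tobacco. The two differ for a person who has stopped smoking but uses a non-combusted tobacco product. Section 20.6 turns the absence of a specimen into the outcome of smoking, so that person would be a treatment failure because of a procedure and not because of smoking.

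The pilot's abstinence rates, odds ratio and number needed to treat (sections 3.1 and 20.4) are meant to guide a full-scale trial. Staff also have two current instructions, in 13.3 and 16.5, that cannot both be followed for such a person. Whether the person is tested could depend on which section a staff member follows.

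**Working it through.** The plan states no figure on this point, so there is nothing to reproduce. The check is a comparison of the texts, followed by an illustration of size.

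**1. The rules side by side.**

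| Section | Function | Condition |
|---|---|---|
| 2.2, 3.2 | Endpoint | No smoking in 7 days |
| 13.3 | Request for specimens | No tobacco products (no look-back period given) |
| 16.5 | Mailed saliva kit | No smoking in 7 days |
| 20.6 | Coding | Smoker unless abstinence is reported and biochemically evidenced |

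**2. Three participants followed through the rules.**

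- No tobacco of any kind: meets both triggers, is tested, and is coded on the result.
- No smoking, uses smokeless tobacco: meets the endpoint's behavioural definition but fails the 13.3 trigger. No specimen is requested, so 20.6 makes this person a smoker. Under 16.5 a person unable to travel would be sent a kit.
- Stopped cigarettes, smokes another tobacco product: fails the endpoint itself. Counting this person as a smoker is correct.

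Only the second person is miscoded. Sections 5.2 and 5.3 allow such a person to enrol.

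**3. Would changing the trigger be enough?** Not alone. Tested in person, the second participant could give a negative CO and a positive cotinine. No section says how that pair is coded. With mailed saliva there is only cotinine, which cannot separate smokeless use from smoking. Section 17.2 says cannabis reports help to interpret the tests, but gives no coding rule. The schedule in 13.2 already collects recent tobacco, alcohol and cannabis use and treatment use at week 26 and at the verification visit, so the information needed for a rule will exist.

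**4. Illustration of size.** Inputs: standard-care abstinence 21.5% (the less intensive arm of the cancer-patient trial cited in 2.5), odds ratio 1.50 (3.3) and 25 per arm (4.3). The share m of quitters miscoded is an assumption, because the documents give no rate of other-product use among quitters.

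- Standard-care odds: 0.215/0.785 = 0.2739. Times 1.50 = 0.4108. Enhanced rate: 0.4108/1.4108 = 29.1%.
- Difference: 29.12 − 21.50 = 7.62 points. Standard error: √[(0.2912×0.7088 + 0.215×0.785)/25] = 12.25 points. 95% interval: 7.62 ± 1.96×12.25, or −16.4 to +31.6 points.
- With equal miscoding, each observed rate is p×(1−m):

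| m | Enhanced | Standard | Difference (points) | Odds ratio | Number needed to treat |
|---|---|---|---|---|---|
| 0 | 29.1% | 21.5% | 7.62 | 1.50 | 13.1 |
| 10% | 26.2% | 19.4% | 6.86 | 1.48 | 14.6 |
| 20% | 23.3% | 17.2% | 6.10 | 1.46 | 16.4 |
| 30% | 20.4% | 15.1% | 5.33 | 1.45 | 18.7 |

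- If 20% were miscoded in one arm only, the odds ratio would be 1.11 (enhanced arm) or 1.98 (standard arm). Nothing in the documents points to such an imbalance.
- In whole people, 7/25 against 5/25 gives (7/18)/(5/20) = 1.56, with 95% interval exp[ln 1.556 ± 1.96×√(1/7+1/18+1/5+1/20)] = 0.42 to 5.78. Recoding one enhanced-arm quitter gives (6/19)/(5/20) = 1.26. Recoding one standard-arm quitter gives (7/18)/(4/21) = 2.04. One in each gives (6/19)/(4/21) = 1.66. All lie well inside the interval.

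**The case against.** The strongest reply is that 13.3 is loose wording. The protocol often uses tobacco and smoking interchangeably, for instance where 13.4 requires a tobacco use status that means current smoking. Section 16.5 has the right trigger, and the follow-up survey that would put the question to participants was uploaded separately and cannot be seen here. This stands as a reason for caution about practice. It does not remove the conflict, because 13.3 states the tobacco restriction twice and is the section that directs collection.

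A second reply is that unverified quitters are not lost from view. Section 20.2 plans self-reported point-prevalence abstinence at 6 months, which would count them as abstinent, and 20.6 varies the share of unverified people assumed abstinent. This largely stands: no separate new sensitivity analysis is needed. Neither provision changes the primary coding, and neither tells people who were never asked for a specimen from those who did not supply one.

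Four stronger readings are tempting, and the documents do not support them:

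- *Any quitter using another tobacco product is miscoded.* The endpoint is no smoking, so users of other combusted tobacco are rightly counted as smokers.
- *The sections contradict each other on which tests count.* Sections 13.1 to 13.3 describe one scheme: CO plus urine in person, or mailed saliva. The wording in 3.4 can summarise those routes, and 7.5 is only a payment schedule. The lack of a cotinine cut-off, and the appearance of the only CO level (above 5 ppm) in 18.1 on feedback to participants, are missing detail and not contradiction.
- *The treatment comparison is biased.* No difference between arms in other-product use is shown.
- *The future trial would be wrongly sized.* That rests on an assumed miscoding share. If the later trial kept the same verified endpoint, the verified rates would be the right planning input.

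**Conclusion.** The point holds in a limited form. Section 13.3 conflicts with the primary endpoint and with 16.5. Through 20.6, the conflict would count a non-smoking user of non-combusted tobacco as a smoker without a test. Whether e-cigarettes fall under the 13.3 restriction is not stated.

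The conclusion rests on reading 13.3 literally, and the unseen survey could show that practice differs. The number affected is unknown. On the assumed shares, equal miscoding moves the difference by 0.8 to 2.3 points, against a 95% half-width of about 24 points. It is a defect in how the primary endpoint is put into operation and not a demonstrated bias. Severity is minor to moderate, and it merits correction because the change is small and is best made before outcomes are coded.

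**What to change.** 1. In section 13.3, request specimens from everyone who reports no smoking in the past 7 days at the week-26 call, matching 2.2, 3.2 and 16.5.
2. In sections 3.4 and 20.6, add one coding sentence, fixed before outcomes are coded. It should say how a negative CO with a positive cotinine is classified for participants reporting non-combusted tobacco or nicotine use, drawing on the use data already scheduled in 13.2. It should also say how such a person is handled when only mailed saliva is available.
3. Flag participants already assessed under the present 13.3 trigger. Use the self-reported 6-month outcome planned in 20.2 as the comparison with the verified rate, by arm.

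The cost is protocol wording and a few extra tests of kinds already planned. There are two downsides. For these participants verification would lean on CO, which by section 18.1 reflects only the past 1 to 2 days against a 7-day endpoint. Verification would also be mixed if some have already passed week 26 and cannot be retested.

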14.0 Comparison of usual care and study procedures

14.1 Alternatives to participation.

The current standard of care for treating tobacco use at UW Health is to electronically refer patients to the Wisconsin Tobacco Quit Line if patients consent to such referral. Clinicians are also able to prescribe smoking cessation pharmacotherapies, including nicotine patches, varenicline, other

PROTOCOL TITLE: Comparative Effectiveness Trial of Tobacco Cessation Treatments among Cancer Patients who Smoke

forms of nicotine replacement therapy, and/or bupropion and to provide smoking cessation counseling to patients.

The proposed study will proactively offer patients both these standard forms of care available at UW Health and will present the option to screen for and possibly enroll in the proposed CET. These alternatives will be presented on an even footing to prospective participants, with all options presented before asking patients to choose among them.

Proactive outreach will occur because evidence suggests that existing standard care options (Quit Line referral, UW Health clinician intervention) are delivered rarely to patients. The proactive model of treatment offers seeks to address this issue that limits the reach of evidence-based smoking treatment by making outreach regarding tobacco treatment options the default, unless the patient opts out of such contacts.

The CET recruitment and consent process will highlight differences between standard care and the treatments offered in the CET, and will clearly identify procedures that are just for research (e.g., assessments, biochemical verification). The CET has also been designed so that participants in both arms will receive treatment that meets the current standard of care available through the Wisconsin Tobacco QuitLine. In addition, participants in both CET arms will receive information about available QuitLine and NCI-sponsored text messaging program (SmokefreeTXT) resources available to them. As such, no patients will be assigned to a condition that offers less than standard care to address their smoking, and participating in the study will not inhibit participants' ability to take advantage of publicly funded smoking cessation treatment resources.

The alternative to participating in the qualitative interview is simply not to participate, and this will not affect the care the patients receive or any other aspect of their relationships with UW Health, UW CCC, or UW more broadly.

14.2 Standard of care.

The current standard of care for treating tobacco use at UW Health is to electronically refer patients to the Wisconsin Tobacco Quit Line if patients consent to such referral. Clinicians are also able to prescribe smoking cessation pharmacotherapies, including nicotine patches, varenicline, other forms of nicotine replacement therapy, and/or bupropion and to provide smoking cessation counseling to patients. Quitline reports and past projects suggest that this standard of care is not being applied consistently, and that relatively few patients are receiving such care.

14.3 Research procedure overlap with standard practice.

PROTOCOL TITLE: Comparative Effectiveness Trial of Tobacco Cessation Treatments among Cancer Patients who Smoke

As noted above, the current standard of care for addressing tobacco use at UW Health is to refer patients to the Wisconsin Tobacco Quit Line, and there is an order set clinicians can use to place orders for pharmacotherapies to help patients stop smoking. These tools are rarely used, however. All patients contacted by UW-CTRI will hear about these standard care options, and will still have these options, and more (e.g., SmokefreeTXT, no-cost pharmacotherapies) available to them if they enroll in the CET. To ensure that study treatments do not interfere with standard care, UW Health primary care providers and oncologists of patient care teams will be able to review and disapprove study medications, and UW Health prescribers will be able to see which study medications were dispensed to patients in Health Link. No other research procedures (e.g., assessments, counseling calls) overlap with standard care activities, and none should interfere with standard care.

14.4 Research participation effects on standard clinical care.

Participation in this research will not affect standard clinical care. Patients will remain eligible for standard smoking cessation treatment, and standard cancer treatment, without delay or disruption.

